7.6 Adverse Event Reporting

The definitions of Adverse Events (AEs) and the subtypes are provided in **Section 8** of the study protocol. Adverse events will be classified by the investigator as to:

- Anticipated vs unanticipated
- Serious vs not serious
- Expected Treatment Effect (ETE) vs Adverse Event (AE)
- Severity: mild, moderate, severe
- Device causality: not related, related, undetermined
- Procedure causality: not related, related, undetermined.

7.7 TEN Testing of Sensory Nerves

Compares sensation in injured/non-injured areas in response to light-moving touch where 10/10 is normal and 0/10 is no sensation. TEN Testing will be performed as follows:

- Light moving touch (examiner’s finger) is applied to the area to be tested as well as to an area of normal sensation (such as arm).
- The subject is asked to rate the best level of sensation they feel in the test area.

- Ten is normal sensation, diminished sensation is rated on a scale of 0-10, with 0 being no sensation, 5 being half of normal, 10 being full sensation.

Subjects experiencing sensory nerve adverse events will be considered resolved when their TEN Testing score is documented as returning to a 10/10 score.

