6.3 Study Procedure

On the day of the procedure and prior to the study procedure, female subjects with child-bearing potential must complete a urine pregnancy test (result must be obtained prior to the procedure).

Medications at investigator discretion may be provided as follows:

- Optional for Procedure (given within 90 minutes prior to procedure):
 - Ativan 2mg or Valium 10-20mg
 - Norco 5-10mg, Hydrocodone 5-10mg, or Ultram 200mg

A responsible driver (friend or family member) is required if these medications are prescribed.

During the study procedure, subjects will be treated with the Renuvion APR device according to the product IFUs and procedures described in this section of the protocol. The bilateral treatment area includes the tissue of the neck (to the posterior border of the sternocleidomastoid muscle) and submental area. Treatment will be performed through three (3) incisions (2 periauricular and 1 submental) with each incision large enough to allow for gas egress, see **Figure 1**. Each incision site will be anesthetized with 1% or 2% Lidocaine with Epinephrine (1:100,000) prior to incision being made.

[figure not shown]

Figure 1: Treatment incisions (2 periauricular and 1 submental).

The treatment area will be infused with standard of care tumescent solution referred to as a Klein solution. The solution consists of 1% or 2% Lidocaine (Plain) to make a 0.2% concentration (double Klein) and Epinephrine 1mg/1ml (1:1,000) and optional Sodium Bicarbonate 8.4% added to Normal Saline or Lactated Ringers. Infuse area with 150-250cc or until the area is taut. To prevent lidocaine toxicity, 35-55mg/kg should not be exceeded¹⁶.

Once infused with Klein solution, undermining of the tissue in the area to be treated will be performed using a cannula 3-4mm in diameter. No energy (i.e. radiofrequency, ultra-sound, or laser energy) or suction will be used during the undermining of the tissue.

After undermining, the Renuvion APR device treatment will be performed using 4-6 treatment passes with settings of 70% power and 1.5 LPM of helium flow with an activation speed of approximately 1-3 cm/s. Prior to performing treatment through each one of the three (3) incisions, the investigator will evaluate activation speed by performing the following steps in the sterile field at a safe distance from the subject:

1. Using a sterile ruler, two parallel lines will be drawn in the sterile field that are 10cm apart.

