7.5 Numeric Rating Scale (NRS) (Primary Safety Endpoint)

The study subjects will be asked to complete a 11-point Numeric Rating Scale (NRS) for the level of pain and discomfort associated with the study procedure – to be completed by the subjects on the day of the procedure prior to the procedure, following the procedure, and at all follow-up visits. The average pain score for the entire region treated will be recorded. Directions to subject will be: *“Please rate the average pain you are experiencing in the treatment area on a scale of 0-10, with 0 being ‘Best/No Pain’ and 10 being the ‘Worst Possible Pain’.”*

Pain will be defined in this study as the average pain reported in the treatment area using the following categories: None (Score of 0), Mild (Score of 1-5), Moderate (Score of 6-7), and Severe (Score of 8-10). Classifications of NRS pain scores have been documented in literature²⁰. Moderate and severe pain/discomfort are considered Adverse Events (AE). Severe subject reported pain does not necessarily correlate to a “severe” adverse event classification. Events will be classified by investigator based on clinical evaluation, the effect to daily activities, and mitigation needed as per **Section 8.6** of this protocol.

Subjects experiencing pain adverse events will be considered resolved when their pain score is documented as returning to a 0 score.

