APPENDIX B: SAMPLE STUDY SUBJECT DAILY DIARY*To be completed by study staff:*

Site ID #	Subject ID	Subject Initials	Procedure Date		
					
			First/Middle/Last	Day	Month
					Year

Instructions to subjects:

Please use this form to record any complications after your study procedure. Be sure to complete an entry every day until your 14-day follow-up visit. Please bring this form to your 14-day follow-up visit.

Day X	Date:										
Please rate the average pain you are experiencing in the treatment area on a scale of 0-10, with 0 being 'Best/No Pain' and 10 being the 'Worst Possible Pain'. Please check one box.											
	0	1	2	3	4	5	6	7	8	9	10
Pain											
Please check all boxes that apply to record any expected treatment effects that you are experiencing.											
Expected Treatment Effect	Are you experiencing this event?					Is this causing an impact to your daily activities such as work, sleep, driving, appetite, etc.?					
Swelling		YES		NO			YES		NO		
Redness of the skin		YES		NO			YES		NO		
Bruising		YES		NO			YES		NO		
Touch sensitivity, numbness/tingling, itching		YES		NO			YES		NO		
Firm areas under the skin		YES		NO			YES		NO		
Crackling sound or popping feeling under the skin		YES		NO			YES		NO		
Are there any other complications you are experiencing?	 YES*  NO *If "YES", please call your study doctor to discuss.										
Are you wearing your compression garment 22 hours/day for Days 0 – 3 and at night for Days 4-21 as directed by the Post-Procedure Care Instructions?							 YES  NO				

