9.4 Statistical Analysis of Additional Endpoints

These analyses will be performed by data type as described in **Section 9.1** of this SAP. All analyses will be descriptive (i.e., no hypotheses will be tested). All of the various AE rates will be estimated using methods for time-to-event data for each category of AE, with emphasis on all device- and procedure-related AEs, and serious device- and procedure-related AEs. Analyses are planned as per **Table 5**.

The assessment tools (e.g. the GAIS and Subject Satisfaction Survey) can be found in the study protocol.

Table 5: Analyses of Additional Endpoints

Endpoint Number	Endpoint	Type of Analysis	Comments
1	The improvement in the appearance of lax tissue in the neck and submental region at 90 days compared to baseline as determined by qualitative 2D photography assessment by blinded Independent Photographic Reviewers.	Categorical	This endpoint is identical to the primary effectiveness endpoint except that it is at 90 days; however, no hypothesis will be tested.
2	Subject Modified Global Aesthetic Improvement Scale (GAIS) at 180-day FUV	Categorical	
3	Investigator Modified GAIS at 180-day FUV	Categorical	
4	Subject satisfaction with procedure recorded at the 180-day FUV on the Subject Satisfaction Survey	Categorical and Continuous	Categorical on 1-4 and Continuous on 5

Endpoint Number	Endpoint	Type of Analysis	Comments
5	Quantitative improvement at 180-days as determined by quantitative assessment based on 2D photography: a) Proportion responders (those achieving at least 20 mm ² of lift of the submental region). b) Average mm ² of improvement.	Categorical and Continuous	Categorical on a and Continuous on b
6	Quantitative improvement at 180-days as determined by quantitative assessment based on 3D photography - Average cc of Total Volume change.	Categorical and Continuous	Categorical on a and Continuous on b
7	The evaluation of adverse events up to the 180-day visit following treatment.	Time-to-event	
8	The evaluation of pain scores through the 30-day follow-up visit as reported by the subject on a Numeric Rating Scale (NRS).	Categorical	

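### TEN testing scores the best sensation in an undefined test area and closes the event at 10/10, so a patchy or partly recovered deficit can be recorded as resolved while numbness persists

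*Protocol*

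**What the plan says.** Protocol Section 7.7 states the purpose of the test: "Compares sensation in injured/non-injured areas in response to light-moving touch where 10/10 is normal and 0/10 is no sensation". The examiner strokes the area under test and also an area of normal sensation, for which the arm is the example given. The scoring instruction is "The subject is asked to rate the best level of sensation they feel in the test area". The closure rule is "Subjects experiencing sensory nerve adverse events will be considered resolved when their TEN Testing score is documented as returning to a 10/10 score".

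Section 7.7 gives no map of the test area, no number of sites, no split by side, and no instruction to go back to the same site at later visits. The treated field is large. Section 6.3 says: "The bilateral treatment area includes the tissue of the neck (to the posterior border of the sternocleidomastoid muscle) and submental area".

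Table 1 of the Protocol schedules TEN on the procedure day and at 1, 7, 14 and 30 days, and only as needed at 90 and 180 days. Section 8.1 has the investigator set resolution dates by in-person or remote means, including phone, text and email. Adverse events reach the analysis through additional endpoint 7 in SAP Section 9.4, Table 5: "The evaluation of adverse events up to the 180-day visit following treatment". That analysis is descriptive, using time-to-event methods.

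**The concern.** The test is there to find and follow loss of sensation, yet the instruction records the most favourable value in the area examined. For pain, Section 7.5 chose a different summary: "The average pain score for the entire region treated will be recorded". For sensation, the choice is the maximum, and the closure rule is then applied to that maximum.

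Closure has several consequences:

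- Section 8.1 says it wants accurate durations for adverse events. A false 10/10 shortens them.
- Sections 6.4.2 and 8.1 direct between-visit contacts to subjects whose adverse events are ongoing. The contact days run from 21 to 165. An event closed at the 30-day visit could forgo the eight contacts from day 45 onward.
- With TEN only as needed after day 30, a normal score by then removes one prompt to retest.
- Section 9.2 treats temporary sensory nerve injury as an expected effect, while Section 8.3 makes permanent impairment a criterion for a serious event. Numbness closed too early could go down as temporary.
- SAP Section 3 continues the trial until all adverse events are resolved, so the definition of resolution also bears on when the trial is complete.

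**Working it through.** The documents give no TEN threshold for recording an event, no sensory injury rate and no TEN result, so there is no stated figure to reproduce. The check is of how the scoring rule behaves.

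**Step 1: the rule as a formula.** Let a share *f* of the tested skin have sensation *s*, and let the rest be normal (10).

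- Best = 10 if *f* < 1; best = *s* if *f* = 1.
- Average = 10(1 − *f*) + *s·f*.
- Lowest = *s* for any *f* > 0.

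**Step 2: put in values.** The values of *f* and *s* are assumed for illustration. Section 7.7 itself defines 0 as no sensation and 5 as half of normal.

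| Share affected *f* | Sensation *s* | Best | Average | Lowest |
|---|---|---|---|---|
| 10% | 0 | 10 | 9.0 | 0 |
| 25% | 0 | 10 | 7.5 | 0 |
| 50% | 0 | 10 | 5.0 | 0 |
| 10% | 5 | 10 | 9.5 | 5 |
| 25% | 5 | 10 | 8.75 | 5 |
| 50% | 5 | 10 | 7.5 | 5 |
| 100% | 0 | 0 | 0 | 0 |
| 100% | 5 | 5 | 5 | 5 |

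For example, the average at *f* = 25% and *s* = 5 is 10 × 0.75 + 5 × 0.25 = 8.75. The best score meets the 10/10 criterion in every row with *f* below 100%. It behaves properly only when the whole tested area is affected.

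**Step 3: two readings of the test area.**

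- If the area examined extends beyond the deficit, for example a numb patch with a normal rim, the score is 10/10 from the start.
- If only the injured patch is examined and it is uniformly numb, best and lowest agree and there is no bias. But once half of that patch recovers fully while the other half stays at 5, the score becomes 10 (the *f* = 50%, *s* = 5 row) and the event meets the closure rule. The lowest score would still be 5.

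**Step 4: bound on the count.** Both the injury rate and the share of deficits that are patchy at the time of testing are assumptions. With Phase II n = 65, the number of affected subjects whose TEN score would read 10/10 is 65 × rate × patchy share.

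- Rate 10%: 65 × 0.10 = 6.5 affected, of whom 0 to 6.5 read normal.
- Rate 20%: 13 affected, 0 to 13 read normal.
- Rate 40%: 26 affected, 0 to 26 read normal.

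Each range runs from a patchy share of 0% to 100%. These figures show only that the documents do not fix the size. They are not estimates.

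**Step 5: closure set beside remote determination.** Section 7.7 ties closure to a documented score from a test done with the examiner's finger. Section 8.1 allows resolution to be decided by phone, text or email, where that test cannot be performed. Neither section says how a 10/10 is to be documented in that case.

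**The case against.** The best defence is that the test area naturally means the injured area. Section 7.7 speaks of injured versus non-injured areas, and the normal comparator is a separate site such as the arm. Where the Protocol wants a whole-field score, as for pain, it says so. Nothing states that the entire bilateral field is scored as one area, and the marks in Table 1 show visits, not the number of sites. This stands: it would be wrong to say that one normal spot anywhere in the neck always produces 10/10. It narrows the point but does not remove it, because a normal rim or a recovered spot within the patch has the same effect, and no text excludes it.

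A reader might also infer that nerve injury is under-counted. The documents do not support that. No section makes a TEN score below 10 a condition for recording an event. The daily diary to day 14 has its own item, "Touch sensitivity, numbness/tingling, itching"; Section 8.1 requires an adverse event interview at each follow-up visit and asks subjects to report complications; Section 8.5 records all adverse events and expected effects.

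Three further cautions have weight. Section 8.4 follows events until adequately resolved or explained, and Appendix C extends the contacts to ongoing expected effects, so a subject who still complains of numbness may well be kept open. The TEN case report form is not among the documents and may already record by site. Whether asking for the best level is the instrument's own wording cannot be judged, because Section 7.7 cites no source. None of these changes the written closure rule.

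**Conclusion.** The point holds as a defect in how resolution is measured. Section 7.7 takes the maximum over an area it does not define and closes the event on that maximum, so a patchy or partly recovered deficit can be closed while numbness persists. The direction favours the device, in resolution status and recorded duration. The size ranges from no effect to complete masking on TEN, depending on what examiners treat as the test area and how often deficits are patchy, and the documents settle neither.

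The reach is limited. Neither primary hypothesis test uses TEN, the adverse event analysis is descriptive, and SAP Table 5 names no separate duration analysis. What is affected is the safety description in a pivotal study, and who remains under between-visit contact. The change is worth making because it is cheap and the bias runs one way.

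**What to change.** In Protocol Section 7.7, and on the TEN case report form to match:

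- Define the test area as the affected site or sites, recorded separately for left neck, right neck and submental area.
- Have the subject rate the lowest sensation felt at each site, in place of the best.
- Retest the same recorded site at later visits.
- Apply the existing 10/10 resolution criterion to that lowest score.

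Reconcile Section 7.7 with Section 8.1, so that it is clear how the 10/10 requirement and remote determination of resolution operate together.

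The cost is a wording change, a form revision, a site instruction and slightly longer examinations. Sensory events may appear to last longer, and scores will not be directly comparable with Phase I scores taken under the present wording; the report should say so.

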8 ADVERSE EVENTS ASSESSMENT REPORTING

8.1 Adverse Events Evaluation

Safety evaluations for this study include an interview with the study subject at each follow-up visit by the Investigator or Research Coordinator to elicit information about any medical occurrence that meets the definition of Adverse Event. This information will be documented in CRF without regard for cause or relation to device and/or procedure.

In addition, study subjects will be instructed in the Informed Consent Form, post-procedure take-home instructions, and verbally by study staff to report all complications experienced post study procedure to the site personnel as soon as they occur/are observed. Study staff will ensure that monitoring and management of all adverse events is prioritized. To ensure this, study staff will contact (phone, text, email, video call at subject's preference) all subjects with ongoing Adverse Events at the following time points, as applicable:

- 21 (± 5) days
- 45 (± 5) days
- 60 (± 5) days
- 75 (± 5) days
- 105 (± 5) days
- 120 (± 5) days
- 135 (± 5) days
- 150 (± 5) days
- 165 (± 5) days

Three attempts will be made to contact the subject before considering the subject contact visit missed and protocol deviation recorded. If subjects are unable to be contacted via their preferred method of contact, another method of contact may be utilized.

Subjects may be asked to come into the site at any time to assess adverse events.

Study investigators are provided liberty to mitigate adverse events as deemed necessary per IHC GCP Guidelines E6(R2)4.3.2 which states "During and following a subject's participation in a trial, the investigator/institution should ensure that adequate medical care is provided to a subject for any adverse events related to the trial".

Adverse event resolution dates will be determined by investigator using either in-person or remote (phone, video call, text, email, etc.) examinations or communication with the subject. To ensure the most accurate reporting of adverse event durations, investigators are instructed not to wait until scheduled office follow-up visits to assess resolution.

It is the Investigator's responsibility to determine seriousness, severity, and relatedness of the Adverse Event to the device and procedure using the definitions below.

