9.2 Risks

This treatment modality was designed to inherently minimize the risk to the subject. However, treatment with energy-based modalities (laser, radiofrequency, and plasma devices) produce subsequent heating of the soft tissue that could involve the following commonly Expected Treatment Effects (ETEs): discomfort/pain, edema, erythema, ecchymosis, hypoesthesia, temporary sensory nerve injury (touch sensitivity, itching, temporary numbness/tingling), transient migratory firmness, and temporary and/or transient crepitus.

In addition to commonly expected treatment effects, treatment with the Renuvion APR device could involve the following risks: helium embolism into the surgical site due to inadvertent introduction into the venous or arterial blood supply system, unintended burns (deep or superficial), pneumothorax, temporary or permanent motor nerve injury, ischemia, fibrosis, infection, gas buildup, bleeding, hematoma, seroma, subcutaneous induration, pigmentation changes, increased healing time, unsatisfactory scarring, asymmetry and/or unacceptable cosmetic result.

Subjects using drugs that reduce coagulation (aspirin or NSAIDs) may experience increased bruising or bleeding at the treatment site.

A grounding pad is used to ground/neutralize the electrical current. Subjects undergoing radiofrequency treatment will be kept away from contact with metal parts which are grounded, or which have appreciable capacitance to earth.

Risks associated with tumescent anesthesia (lidocaine and epinephrine) include blurred vision, mental/mood changes, drowsiness, dizziness, unusually slow heartbeat, rash, itching, swelling, anxiety, apprehensiveness, restlessness, tremor, weakness, sweating, palpitations, pallor, nausea and vomiting, headache, and respiratory difficulties.

Side effects and subject instructions for medications that are at investigator discretion include:

- **Keflex**

If any of these effects persist or worsen, tell your doctor or pharmacist promptly:

- Diarrhea
- Nausea
- Vomiting
- Upset stomach

This medication may rarely cause a severe intestinal condition due to resistant bacteria. This condition may occur during treatment or weeks to months after treatment has stopped. Do not use anti-diarrhea or opioid medications if you have any of the following

symptoms because these products may make them worse. Tell your doctor right away if you develop:

- Persistent diarrhea
- Abdominal or stomach pain/cramping
- Blood/mucus in your stool

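### A TEN score back at 10/10 closes a sensory nerve AE, but the scale grades only reduced sensation, so an AE can be recorded as resolved while tingling, itching or touch sensitivity continues

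*Protocol*

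**What the plan says.** Protocol section 7.7 describes the TEN test as a rating of light moving touch in the treated area against an area of normal sensation. The instruction is "The subject is asked to rate the best level of sensation they feel in the test area", and the scale is defined as "Ten is normal sensation, diminished sensation is rated on a scale of 0-10, with 0 being no sensation". The resolution rule in the same section is "Subjects experiencing sensory nerve adverse events will be considered resolved when their TEN Testing score is documented as returning to a 10/10 score". It has no second condition and makes no exception by type of symptom.

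Protocol section 9.2 lists, among the expected treatment effects, "hypoesthesia, temporary sensory nerve injury (touch sensitivity, itching, temporary numbness/tingling". Hypoesthesia is thus a separate item from sensory nerve injury. The daily diary in Appendix B has one yes/no line for "Touch sensitivity, numbness/tingling, itching", under a column for expected treatment effects. Section 7.4 and Appendix B end the diary at the 14-day visit.

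Section 7.6 leaves it to the investigator to classify an event as an ETE or an AE, and gives no threshold for sensory symptoms. Section 8.1 says "Adverse event resolution dates will be determined by investigator using either in-person or remote" examination or communication with the subject. Section 8.4 requires monitoring until events are adequately resolved or explained.

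**The concern.** The category of event and the measure that closes it do not cover the same ground. The protocol's own description of sensory nerve injury includes heightened and abnormal sensations. The only sensory scale grades loss of touch and stops at normal. A subject can have full light touch and still have tingling, itching or hypersensitivity, and the 7.7 criterion takes no account of that.

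What is at stake is the recorded duration and resolution status of sensory nerve AEs for a device that heats tissue under the skin of the neck. Several follow-up provisions depend on an event still being open:

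- the extra contacts between days 21 and 165 (protocol sections 6.4.2 and 8.1);
- follow-up of device-related events beyond the final visit (section 8.5);
- the SAP's statement in section 3 that the trial runs until AEs have resolved.

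**Working it through.** No arithmetic on trial figures applies. The check sets the sections side by side.

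**Step 1. What the scale can show.** Inputs: the symptoms named in 9.2 and the scale in 7.7.

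| Symptom in 9.2 | Place on the TEN scale | Effect of the 7.7 rule if recorded as an AE |
|---|---|---|
| Numbness | Lowers the score below 10 | Event stays open until touch returns; the rule works |
| Tingling | None | 10/10 can be met while it continues |
| Itching | None | 10/10 can be met while it continues |
| Touch sensitivity | None; the scale stops at normal | 10/10 can be met while it continues |

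Of the four named symptoms, one is graded and three are not. Some subjects might lower their rating because of tingling, but nothing tells them to. The score would then mean different things for different subjects.

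**Step 2. The size of the error for one event.** Let t0 be onset, tT the date the TEN score is back at 10/10, and tS the date the last symptom of that event ends.

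- Duration under 7.7: tT − t0
- Duration of the event: max(tT, tS) − t0
- Shortfall: max(0, tS − tT)

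The shortfall is zero when numbness is the only symptom and ends as touch returns. It is positive whenever tingling, itching or touch sensitivity outlasts the loss of touch. The documents give no values for tT or tS, so the shortfall cannot be put in days.

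**Step 3. Whether another section overrides the rule.** Section 8.1 says who sets the date and by what means; section 8.4 says monitoring continues until resolution. Neither says that a persisting symptom keeps a sensory event open at 10/10. Section 8.1 also allows phone, text or email, by which the examiner's-finger test in 7.7 cannot be done. The two sections are therefore unreconciled.

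**Step 4. Comparison with the protocol's other resolution rules.** Pain AEs close when the pain score itself is 0 (7.5). Motor nerve AEs close when the findings are back to baseline (7.8). Of the three, only the sensory rule uses a measure that misses part of its own category.

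**Step 5. What else would record the symptom.** The diary has the right item but ends at the 14-day visit and is not linked to resolution. Table 1 schedules TEN testing through day 30 and only as needed at days 90 and 180. AE assessment is scheduled at every visit, so a persisting symptom can be picked up again. No rule says whether the closed event would then be reopened.

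**The case against.** Four points on the other side have force.

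- **These symptoms are listed as ETEs.** Section 9.2 and the diary both present them that way, while the 7.7 rule covers AEs. A reader might infer that the rule closes every report of tingling or itching. It does not; it applies only once the investigator has classified the symptom as an AE. Section 7.7 expects such AEs, so the gap remains, but it is narrower than the symptom list suggests.

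- **The symptom does not drop out of sight.** A reader might infer that closing the event ends tracking. Section 8.1 requires an AE interview at every follow-up visit. Appendix C tells subjects that the day 21 to 165 contacts also cover ongoing ETEs, whereas sections 6.4.2 and 8.1 mention only AEs. Section 8.5 follows device-related ETEs as well as AEs still open at the final visit. Painful sensitivity can also register on the NRS. What stands is that follow-up could end early for an event marked resolved, not that it must.

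- **The rule speaks of a return to 10/10.** That presupposes an earlier score below 10. A reader might infer that a hypersensitivity-only event would be recorded with zero duration. The wording fits such an event poorly, and sections 8.1 and 8.4 more naturally govern it. The firm case is numbness that gives way to tingling or touch sensitivity.

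- **A careful investigator can keep the event open under 8.1.** True, but 7.7 states the specific criterion and nothing says which section prevails, so sites may differ.

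**Conclusion.** The point holds as a gap in how resolution is recorded. Followed as written, section 7.7 can close a sensory nerve AE while a symptom that section 9.2 places in the same category continues. Recorded durations could be too short. The documents do not support a statement that they will be biased downward, because neither the frequency of such AEs nor investigators' practice under 8.1 is known. The number of subjects affected cannot be derived.

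The consequence is limited to AE duration, resolution status and the follow-up tied to them. Neither primary endpoint uses the TEN score, and the sample size does not depend on it. SAP section 9.4 plans AE rates by time-to-event methods and names no analysis of duration or resolution, so rates counted from onset are unaffected. The conclusion assumes that at least some sensory symptoms are classified as AEs and that sites apply the 7.7 criterion literally.

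**What to change.** Reconcile 7.7 with 8.1 and 9.2. Record a sensory nerve AE as resolved only when both conditions are met:

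1. the TEN score is 10/10; and
2. the subject reports that the sensory symptoms recorded for that AE, or that followed from it, are gone. These are touch sensitivity, tingling or itching that the investigator attributes to the sensory nerve event.

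The resolution date is the later of the two. The attribution condition is needed because 9.2 also lists itching as a risk of the tumescent anesthesia and as a sign of drug allergy; without it, unrelated itching would hold nerve events open.

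Collect the second condition with one yes/no CRF item at each visit or contact while the event is open. The diary wording can be reused, but the diary itself cannot, since it stops at day 14. Also align sections 6.4.2 and 8.1 with Appendix C on whether the contacts between visits cover ongoing ETEs.

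Cost: one sentence in 7.7, one CRF item, and somewhat longer reported durations. The TEN half of the rule still needs an in-person examination, as it does now.
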